**PROTOCOL AMENDMENT SUMMARY OF CHANGES TABLE**

DOCUMENT HISTORY	
Document	Date
Amendment 6	This document
Amendment 5	01 October 2021
Amendment 4	30 July 2021
Amendment 3	14 August 2020
Amendment 2	07 May 2020
Amendment 1	10 April 2020
Original Protocol	12 February 2020

## 1. PROTOCOL SUMMARY

### 1.1. Synopsis

A Phase 2 Randomized, Open-label, Parallel-group, Multicenter Study to Assess Intrahepatic and Peripheral Changes of Immunologic and Virologic Markers in Response to Combination Regimens Containing JNJ-73763989 and Nucleos(t)ide Analog With or Without JNJ-56136379 in Patients With Chronic Hepatitis B Virus Infection.

JNJ-73763989 (JNJ-3989) is a liver-targeted antiviral therapeutic for subcutaneous (SC) injection designed to treat chronic hepatitis B virus (HBV) infection via a ribonucleic acid interference (RNAi) mechanism. Engagement of the cellular RNAi machinery by JNJ-3989 results in specific cleavage of HBV ribonucleic acid (RNA) transcripts, thereby reducing the levels of HBV proteins and the pre-genomic RNA (pgRNA), the precursor of viral relaxed circular deoxyribonucleic acid (DNA). The RNAi triggers in JNJ-3989, JNJ-73763976 (JNJ-3976) and JNJ-73763924 (JNJ-3924), are designed to target all HBV RNA transcripts derived from covalently closed circular DNA (cccDNA), as well as transcripts derived from integrated viral DNA. The latter has been suggested to be a significant source of hepatitis B surface antigen (HBsAg) in hepatitis B e antigen (HBeAg) negative patients or patients on long term treatment with nucleos(t)ide analogs (NAs), the current standard of care.

JNJ-56136379 (JNJ-6379) is an orally administered capsid assembly modulator (CAM) that is being developed for the treatment of chronic HBV infection. JNJ-6379 binds to hepatitis B core protein (HBC) and interferes with the viral capsid assembly process, thereby preventing the polymerase-bound pgRNA encapsidation. This results in the formation of HBV capsids, devoid of HBV DNA or RNA (non-functional capsids), and ultimately in the inhibition of HBV replication. In addition, JNJ-6379 also acts at an early stage of the viral life cycle by inhibiting the de-novo formation of cccDNA potentially by interfering with the capsid disassembly process. JNJ-6379 was initially part of the study intervention for participants but has been removed as study intervention with the implementation of an urgent safety measure, as described in Protocol Amendment 5.

Prior to Protocol Amendment 5: The term “study intervention” throughout the protocol, refers to JNJ-3989, JNJ-6379, NA, and optional PegIFN- $\alpha$ 2aa.

As of Protocol Amendment 5: The term “study intervention” throughout the protocol, refers to JNJ-3989, NA, and optional PegIFN  $\alpha$ 2a.

## OBJECTIVES AND ENDPOINTS

The study will be conducted in 3 phases for all participants: a screening phase (4 weeks), an open-label study intervention phase (48 weeks), and a follow-up phase (48 weeks). Note that the follow-up period will be extended for participants who are receiving optional treatment with PegIFN- $\alpha$ 2a and who meet NA treatment completion criteria at the end of treatment with NA and PegIFN- $\alpha$ 2a to ensure all participants have at least one year of follow-up after NA treatment cessation.

The following objectives and endpoints will be assessed overall and by study panel:

Objectives	Endpoints
Primary	

 
To assess changes in intrahepatic HBsAg between baseline and on-treatment liver
 
	
 
Changes in the proportion of HBsAg positive hepatocytes between baseline and on-treatment Week 40
 

a Note: Optional PegIFN  $\alpha$ 2a was introduced as ‘study intervention’ as of Protocol Amendment 4.

Objectives	Endpoints
biopsy in response to JNJ-3989-based combination treatment	
Secondary	

 
To assess changes in intrahepatic immune response between baseline and on-treatment liver biopsy
 
	
 
Changes between baseline and on-treatment liver biopsy in intrahepatic immune response (eg, CD45+ T-cells, CD4+ T-cells, CD8+ T-cells, Natural Killer cells, and dendritic cells) in terms of proportion of cells, cell types, and spatial redistribution
 

 
To assess changes in intrahepatic viral nucleic acids and proteins between baseline and on-treatment liver biopsy
 
	
 
Changes from baseline in intrahepatic viral parameters (such as cccDNA, pgRNA, intrahepatic RNA, or HBsAg in terms of copy number, or number of positive cells)
 
Changes from baseline in intrahepatic cccDNA levels and transcriptional activity (pgRNA/cccDNA ratio)
 


 
To evaluate the efficacy of the study intervention as measured in blood
 
	
 
The proportion of participants during the study intervention and follow-up phases with:           
 
HBsAg seroclearance at Week 72 (ie, 24 weeks after completion of all study interventions at Week 48) without restarting NA treatment.
 
(Sustained) Reduction, suppression, and/or seroclearance considering single and multiple markers (such as HBsAg, HBeAg, HBV DNA and ALT)
 
HBsAg and HBeAg seroconversion
 
Flares (virologic, biochemical, and clinical)
 
 
 
Time to first HBsAg seroclearance
 

 
To evaluate the frequency of virologic breakthrough during study intervention
 
	
 
Proportion of participants with virologic breakthrough
 

 
To assess HBV-specific T-cell responses
 
	
 
Changes from baseline in HBV-specific peripheral blood T-cell responses during the study intervention and follow-up phases
 

 
To evaluate the safety and tolerability of the study intervention
 
	
 
Proportion of participants with (S)AEs and abnormalities in clinical laboratory tests (including hematology, blood biochemistry, blood coagulation, urinalysis, urine chemistry, and renal biomarkers), 12-lead ECGs, vital signs, and physical examinations throughout the study
 

 
To evaluate the plasma PK of JNJ-3989 (ie, JNJ-3976 and JNJ-3924) and
 
	
 
Plasma PK parameters of JNJ-3976, JNJ-3924, and optionally of JNJ-6379, NA and PegIFN-<math>\alpha</math>2a, as applicable
 

Objectives	Endpoints
optionally of JNJ-6379, NA and PegIFN- $\alpha$ 2a, as applicable	
Exploratory	

 
To explore the relationship of intrahepatic markers with blood markers (immune and viral)
 
	
 
Association between levels and changes in intrahepatic and blood markers
 


 
To explore the association of baseline characteristics and intrahepatic and/or blood (immune and viral) biomarkers at baseline and on/off-treatment with selected on/off-treatment efficacy variables
 
	
 
Association of baseline characteristics and baseline and on/off-treatment viral blood markers (such as baseline NA treatment duration, age, and baseline and on/off-treatment HBsAg levels) with selected off-treatment efficacy variables
 
Association of intrahepatic and blood biomarkers (such as cccDNA levels, T-cell frequency) with selected on/off-treatment efficacy variables
 

 
To explore intrahepatic immune and viral changes at Week 72 and/or during off-treatment flares (only for participants with Week 72 biopsy available)
 
	
 
Changes from baseline and on-treatment liver biopsy in intrahepatic immune and viral markers at Week 72 and/or during off-treatment flares (only for participants with Week 72 biopsy available)
 

 
To explore changes in the severity of liver disease
 
	
 
Changes in fibrosis (according to Fibroscan liver stiffness measurements) at the end of study intervention (EOSI) and end of follow-up versus screening/baseline*
 

 
To explore the efficacy in terms of changes in HBV RNA and hepatitis B core-related antigen (HBcrAg) levels.
 
	
 
Changes from baseline in HBV RNA and HBcrAg levels during study intervention and follow-up phases.
 

 
To explore the relationship between plasma PK parameters (JNJ-3989 [ie, JNJ-3976 and JNJ-3924] and/or JNJ-6379 and/or NA and/or PegIFN-<math>\alpha</math>2a) and selected pharmacodynamic (PD) parameters of efficacy and/or safety, as applicable
 
	
 
Relationship between various plasma PK parameters (JNJ-3976 and JNJ-3924, and/or JNJ-6379, and/or NA, and/or PegIFN-<math>\alpha</math>2a) and selected efficacy and/or safety endpoints, as applicable
 


 
To explore the HBV genome sequence
 
	
 
The emergence of intervention-associated mutations during the study intervention and follow-up phases
 
To assess the impact of baseline HBV genome polymorphisms on selected on/off-treatment efficacy variables
 

\* Only applicable to participants who are enrolled at a site with an on-site Fibroscan device.

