### **Changes in Intrahepatic Viral Nucleic Acids and Proteins**

Changes from baseline in cccDNA level and/or transcriptional activity will be assessed using the general considerations outlined above.

Furthermore, the difference in the level of infected hepatocytes at baseline will be assessed by comparing cccDNA level and/or transcriptional activity.

Analyses of other viral markers will be performed descriptively. Statistical analyses will depend on the assay technology applied and the scope of the analyses.

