5.4.1.2. Intrahepatic Viral Parameters

5.4.1.2.1. For Panels 1 and 2

Descriptive statistics on actual values at baseline and Week 40 and changes from baseline at Week 40 will be summarized for the following parameters:

- Number and proportion of cccDNA-positive hepatocytes
- Number and proportion pgRNA-positive hepatocytes
- Number and proportion of silent hepatocytes
- cccDNA levels (positive/negative)
- pgRNA levels (positive/negative)

Number of cells will be expressed in original unit and proportions or ratios will be provided in both original and \log_{10} transformed scales. Change from baseline will be provided in \log_{10} transformed unit. In addition, same graphical displays as described in Section 5.3.1.2.3 will be provided.

5.4.1.2.2. For Panel 3

The number and proportion of HBsAg+ hepatocytes, as well as the same viral parameters described in Section 5.4.1.2.1, may be provided at Week 12 and Week 40, depending on the availability of biopsy material.

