5.5. Exploratory Endpoints Analysis

5.5.1. Relationship Between Intrahepatic and Blood Markers

Relationships between intrahepatic and blood markers (Table 4) and/or their change from baseline at Week 40 will be evaluated graphically with scatter plots displaying individual associations.

Means on pooled individual data by study panel and overall mean will also be plotted on the same graph.

The following correlation coefficients will be calculated by study panel and overall for the different correlation scenarios:

- Pearson's correlation coefficient for two continuous variables.
- Phi correlation coefficient for two binary variables.
- Point biserial correlation coefficient for one binary variable and one continuous variable.

Potential relationship on the selected subgroups defined in Section 5.7.4 will also be explored using the same graphical approach.

The following markers will be considered, i.e., each intrahepatic marker will be plotted against each blood marker:

Table 4: List of Intrahepatic and Blood Markers of Interest

Intrahepatic Markers/Endpoints	Blood Markers/Endpoints
• Proportion of HBsAg+ hepatocytes at Week 40	• HBV DNA level at Week 40 (\log_{10})
• Change from Baseline at Week 40 in proportion of HBsAg+ hepatocytes	• HBV RNA level at Week 40 (\log_{10}) • HBsAg level at Week 40 (\log_{10})

 • Proportion of cccDNA-positive hepatocytes at Week 40 • Change from Baseline at Week 40 in proportion of cccDNA-positive hepatocytes • Proportion of pgRNA-positive hepatocytes at Week 40 • Change from Baseline at Week 40 in proportion of pgRNA-positive hepatocytes • pgRNA levels at Week 40 (\log_{10} copies/ cell) • Change from Baseline at Week 40 in pgRNA levels (\log_{10} copies/ cell) • 	
 • HBeAg level at Week 40 (\log_{10}) • HBcrAg level at Week 40 (\log_{10}) • Change from Baseline at Week 40 in HBV DNA (\log_{10}) • Change from Baseline at Week 40 in HBV RNA (\log_{10}) • Change from Baseline at Week 40 in HBsAg (\log_{10}) • Change from Baseline at Week 40 in HBeAg (\log_{10}) • Change from Baseline at Week 40 in HBcrAg (\log_{10}) • Maximum on-treatment ALT decrease • HBsAg seroclearance at FU Week 24
--	---

Additional markers and endpoints may be evaluated when data will be available.

5.5.2. Association Between Baseline Characteristics or Intrahepatic/Blood Markers with Efficacy Variables

The following list of efficacy endpoints of interest will be evaluated:

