6.2. Appendix 2 Changes to Protocol-Planned Analyses

No change from protocol-planned analyses.

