6.3.2. Baseline Characteristics

Table 9 presents a list of the baseline characteristics variables that will be summarized by study panel and overall for the ITT and Safety analysis set (only if ITT and Safety Analysis sets are different).

Table 9: Baseline Characteristics Variables

Continuous Variables	Summary Type
HBV history	
Duration of infection (years) = (treatment start date – date of HBV infection +1)/365.25; rounded to 1 decimal	
Time since HBV diagnosis (Years) = (treatment start date – date of HBV diagnosis+1)/365.25; rounded to 1 decimal	
Duration of NA at baseline (years)	
HBV viral activity and serology parameters	

Continuous Variables	Summary Type
HBeAg at baseline in IU/mL and log10 IU/mL (for HBeAg positive participants only at study entry)	
HBsAg at baseline in IU/mL and log10 IU/mL	
HBV DNA at baseline in IU/mL and log10 IU/mL	
HBV RNA at baseline: values in copies/mL and log10 copies/mL	
HBcrAg at baseline in log U/mL	
HBsAg Antibody (Anti-HBs) at baseline in mIU/mL and log10 mIU/mL	
Fibrosis score	
HBV intrahepatic viral parameters	
Proportion of HBsAg+ hepatocytes at baseline, derived as number of HBsAg+ hepatocytes * 100 / total number of evaluated hepatocytes	Descriptive statistics (N, mean, standard error [SE], standard deviation [SD], median and range [minimum and maximum], and IQ range).
Proportion of cccDNA-positive hepatocytes, derived as number of cccDNA-positive hepatocytes * 100 / total number of evaluated hepatocytes	
Proportion of pgRNA-positive hepatocytes, derived as number of pgRNA-positive hepatocytes * 100 / total number of evaluated hepatocytes	
pgRNA/cccDNA ratio (transcriptional activity)	

 • Proportion infected with active transcription • <1.6 cccDNA copies and active transcription • Infected without HBV transcription: silenced hepatocytes • Non-infected hepatocytes (LLOD 1.6 copies/cell) 	
RNA levels (copies / cell)	
Proportion of immune cells at baseline	
Categorical Variables	Summary Type
HBV history	
Mode of HBV infection: Sexual transmission, intravenously injectable drug use, blood transfusion, Hemophilia-associated injection, occupational exposure, mother to child transmission, unknown and other	
Treatment history: not currently treated, virologically suppressed	
History of IFN-alpha : Yes, No	
History of Lamivudine, Telbivudine, Adefovir : Yes, No	
Has never received HBV treatment (only for currently not treated participants): Yes, No	

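### SAP 5.4.1.2.1 gives no pgRNA/cccDNA ratio and no copies per cell at Week 40, although a secondary endpoint names the ratio and Appendix 2 declares no change

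*Protocol*

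**What the plan says.** The objectives tables of the protocol (Synopsis and Section 3) and of the SAP (1.1.1) carry two endpoints on intrahepatic virus. One covers viral parameters in general, measured "in terms of copy number, or number of positive cells". The other is specific: "Changes from baseline in intrahepatic cccDNA levels and transcriptional activity (pgRNA/cccDNA ratio".

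SAP 5.4.1.2.1 is the section that analyses them for Panels 1 and 2. It summarises five items at baseline, at Week 40 and as change: number and proportion of hepatocytes positive for cccDNA, positive for pgRNA, and silent, then "cccDNA levels (positive/negative") and "pgRNA levels (positive/negative").

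Quantitative forms appear in two other places:
- SAP Table 4 (5.5.1), for exploratory scatter plots and correlations with blood markers, lists the Week 40 value and "Change from Baseline at Week 40 in pgRNA levels", in log10 copies per cell.
- SAP Table 9 (6.3.2), for baseline characteristics, lists "pgRNA/cccDNA ratio (transcriptional activity") with four classes beneath it, and RNA in copies per cell.

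SAP Appendix 2, on departures from the protocol, reads in full: "No change from protocol-planned analyses."

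**The concern.** The protocol itself defines transcriptional activity as the pgRNA/cccDNA ratio. If the SAP is followed as written, that ratio is described at baseline and never again, so its change from baseline goes unreported as a secondary endpoint.

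The remaining secondary items are all threshold-based: each cell is positive or not, silent or not. JNJ-3989 acts by cleaving HBV RNA (protocol synopsis), and protocol 2.1 gives characterising the mode of action as a use of these analyses. A cell that goes from many RNA copies to a few, still above the threshold, counts as positive at both visits. A graded reduction of that kind is what copies per cell would show and a positive-cell count may miss.

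A reader of the study report would also rely on Appendix 2 and conclude that every protocol-planned analysis was carried over.

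**Working it through.** The documents attach no test, sample size or expected value to this endpoint, so there is no figure of the plan to reproduce. The check is a comparison of sections, followed by an illustration under stated assumptions.

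**1. Endpoint against analysis**

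| Part of the endpoint | SAP 5.4.1.2.1 (secondary) | Elsewhere in the SAP |
|---|---|---|
| cccDNA level | positive/negative; positive-cell count and proportion | one Table 9 class uses a cut at 1.6 copies |
| pgRNA level | positive/negative; positive-cell count and proportion | Table 4: log10 copies per cell, Week 40 and change (exploratory) |
| pgRNA/cccDNA ratio | not listed; silent cells are a coarse proxy | Table 9: ratio and four classes, baseline only |

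Section 5.4.1.2.1 also does not fit its own list. Its sentence on scales provides for ratios, but no ratio is listed. It puts change on the log10 scale, which cannot apply to a positive/negative variable. The same list is reused for Panel 3 (5.4.1.2.2), whose own objectives name the ratio, and for the Follow-up Week 24 biopsies (5.5.3).

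**2. Do the data exist?**

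The SAP's account of Amendment 2 gives two different reasons. Removals from 5.4.1.2 and from Table 4 are put down to data not collected because of laboratory problems. Revisions to 5.5.2 and Table 9 are said to match the data that were collected. Table 9 therefore supports a baseline ratio and baseline copies per cell. At Week 40, copies per cell rests on Table 4 alone, and the 5.5.2 list carries cccDNA and pgRNA only as proportions of positive cells. Availability at Week 40 is open.

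**3. What a threshold summary can miss**

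Assumptions, none of which the documents supply:
- pgRNA per cell is log-normal, with mean μ and standard deviation σ on the log10 scale.
- A cell is positive above 1.6 copies. Table 9 gives this limit beside its non-infected class; applying it to pgRNA is an assumption.
- The true effect is a 90% fall, so μ drops by 1.0.

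Positive proportion = 1 − Φ((log10 1.6 − μ)/σ), with log10 1.6 = 0.204. For μ = 2 and σ = 0.5, the argument before treatment is (0.204 − 2)/0.5 = −3.59, giving 100.0%. After the fall it is (0.204 − 1)/0.5 = −1.59, giving 94.4%.

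| Baseline median copies (μ) | σ = 0.5 | Fall, points | σ = 0.8 | Fall, points |
|---|---|---|---|---|
| 1,000 (3) | 100.0% to 100.0% | 0.0 | 100.0% to 98.8% | 1.2 |
| 100 (2) | 100.0% to 94.4% | 5.6 | 98.8% to 84.0% | 14.8 |
| about 32 (1.5) | 99.5% to 72.3% | 27.2 | 94.7% to 64.4% | 30.3 |
| 10 (1) | 94.4% to 34.2% | 60.2 | 84.0% to 39.9% | 44.1 |
| about 3 (0.5) | 72.3% to 8.0% | 64.3 | 64.4% to 18.9% | 45.5 |

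On the log10 scale that the SAP uses for change in proportions, the true fall of 1.0 shows as 0.00 to 0.07 at μ = 2 to 3, and as 0.32 to 0.96 at μ = 0.5 to 1.

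The SAP does not say whether the positive/negative levels are called per cell or per participant. If a participant is positive with at least one positive cell among n, then with 5% of cells positive and n = 100 (assumed) the probability of a positive call is 1 − 0.95^100 = 0.994. Such a call would rarely change.

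**The case against.** Four points stand on the other side.

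- A reader might infer that the endpoint is analysed only as positive/negative. The documents do not support that. Three of the five items are graded per participant, and the general viral endpoint expressly allows positive-cell counts as an alternative to copy number.
- Transcriptional activity is not wholly absent at Week 40. Silent hepatocytes correspond to one of the four Table 9 classes, and protocol 9.4.1.2 is worded loosely: "Changes from baseline in cccDNA level and/or transcriptional activity will be assessed using the general considerations outlined above". This loosens the analysis text, but it does not take the ratio out of the objectives tables, which the SAP repeats.
- A reader might take the SAP's Amendment 2 as confirmation that Week 40 copies per cell were collected. The statement about matching collected data is attached to 5.5.2 and Table 9, not to Table 4. The Table 4 entry may be residual text.
- Other read-outs exist. If the data are there, 5.5.1 plots individual and mean changes in pgRNA copies per cell. Blood HBV RNA is summarised over time (5.5.5), and the primary endpoint captures the protein effect in hepatocytes. No hypothesis is tested, so no inferential claim is at risk.

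These points narrow the concern. They do not supply a Week 40 summary of the ratio, and they do not make the Appendix 2 statement correct. Uncertainty about the data cuts both ways: either data exist that the secondary analysis omits, or Table 4 lists a variable that was not measured. Both need a correction.

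**Conclusion.** The point holds as a gap between a named secondary endpoint and its analysis. The SAP has no post-baseline summary of the pgRNA/cccDNA ratio. It confines change in pgRNA copies per cell to exploratory correlations, and it declares no departure from the protocol. This follows from the sections themselves and needs no assumption.

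The cost in information is conditional. A graded RNA reduction above the threshold may be missed. It would be tempting to say that the RNA knock-down is largely hidden, but the documents give no baseline copies per cell, and the illustration runs from no visible change (0.0 points at a median of 1,000 copies) to an obvious one (64.3 points at a median of about 3). The result rests on the log-normal shape, the assumed σ and the use of the 1.6-copy limit for pgRNA.

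The SAP should be corrected. The primary endpoint is not affected.

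**What to change.** In SAP 5.4.1.2.1, where Week 40 data exist, add baseline, Week 40 and change values for:
- pgRNA in log10 copies per cell (the Table 4 variable);
- the pgRNA/cccDNA ratio or, failing that, its four Table 9 classes.

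Present both overall and by panel with 80% CIs, as elsewhere in the SAP, and keep the positive-cell and silent-cell summaries. Where the data do not exist, remove the items from Tables 4 and 9 and say so. In either case, replace the Appendix 2 statement with a list of the protocol endpoint parts that were dropped or could not be measured.

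The cost is SAP wording and a few extra descriptive tables. If the Week 40 values are already held, no new sample or assay is needed; if they are not, the change is one of declaration only.

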## Hypothesis

As this is an exploratory study, no hypothesis will be tested.

## OVERALL DESIGN

As of Protocol Amendment 5, this study is a Phase 2 single-arm, open-label, multicenter, study to assess intrahepatic and peripheral changes of immunologic and virologic markers in response to a combination regimen containing JNJ-3989 and NA in chronic HBV-infected participants.

With the implementation of an urgent safety measure, as described in Protocol Amendment 5, JNJ-6379 has been removed as study intervention and the study will continue as a single-arm study. Participants randomized to Arm 1 had to stop JNJ-6379 treatment immediately but continue JNJ-3989 + NA treatment.

In addition, participants who provide separate consent may receive optional treatment with PegIFN- $\alpha$ 2a starting after the Week 40 biopsy (or after the optional leukapheresis if applicable) but before the Week 48 visit. The duration (either 12 or 24 weeks) will be at the investigator's discretion.

A target of 24 chronic HBV-infected male and female participants, 18-65 years (inclusive) of age will be enrolled in 2 panels, approximately 12 participants in each panel. Panel 1 will consist of participants who are HBeAg positive and not currently treated and Panel 2 will consist of participants who are HBeAg negative and virologically suppressed by entecavir (ETV), tenofovir disoproxil, or tenofovir alafenamide (TAF) treatment.

The study will be conducted in 3 phases for all participants: a screening phase (4 weeks), an open-label study intervention phase (48 weeks), and a follow-up phase (48 weeks). If necessary, eg, for operational reasons, the screening phase may be extended up to a maximum of 6 weeks on a case-by-case basis and in agreement with the sponsor. The duration of individual participation will be up to 102 weeks. Note that the follow-up period will be extended for participants who are receiving optional treatment with PegIFN- $\alpha$ 2a and who meet NA treatment completion criteria at the end of treatment with NA and PegIFN- $\alpha$ 2a to ensure all participants have at least one year of follow-up after NA treatment cessation. For those participants, the duration of individual participation may be extended up to 126 weeks.

Prior to Protocol Amendment 5, participants were randomized in a 1:1 ratio within each panel to receive one of the following interventions (ie, treatments) for 48 weeks:

- Intervention arm 1, combination regimen JNJ-3989+JNJ-6379+NA (target of 12 participants):
  - 200 mg JNJ-3989 (SC injection once every 4 weeks [Q4W], with the last injection at Week 44), AND
  - 250 mg JNJ-6379 (tablets once daily [qd]), AND
  - NA: ETV, tenofovir disoproxil, or TAF (tablets qd)
- Intervention arm 2, combination regimen JNJ-3989+NA (target of 12 participants):
  - 200 mg JNJ-3989 (SC injection Q4W, with the last injection at Week 44), AND
  - NA: ETV, tenofovir disoproxil, or TAF (tablets qd)

As of Protocol Amendment 5:

- Participants who were randomized to study intervention with JNJ-6379 prior to Protocol Amendment 5, had to stop JNJ-6379 treatment immediately but will still receive the following interventions (ie, treatments) for 48 weeks:
  - 200 mg JNJ-3989 (SC injection Q4W, with the last injection at Week 44), AND
  - NA: ETV, tenofovir disoproxil, or TAF (tablets qd)
- New participants will enroll without randomization within each panel to receive the combination regimen JNJ-3989 + NA as study intervention for 48 weeks:

200 mg JNJ-3989 (SC injection Q4W, with the last injection at Week 44), AND

NA: ETV, tenofovir disoproxil, or TAF (tablets qd)

For participants who consented to receive optional PegIFN- $\alpha$ 2a, the PegIFN- $\alpha$ 2a treatment will be completed after 12 or 24 weeks at the investigator's discretion.

All participants will complete treatment with JNJ-3989 after a fixed duration of 48 weeks. If the NA treatment completion criteria (see "Study Intervention Completion at Week 48") are met based on clinical laboratory tests performed at Week 44, treatment with NA will also be completed at Week 48. In participants not meeting these criteria, NA treatment will continue during the follow-up phase. Participants who are receiving optional treatment with PegIFN- $\alpha$ 2a and who have not met NA treatment completion criteria at Week 48 may have NA treatment completion criteria assessed at the end of treatment with PegIFN- $\alpha$ 2a and stop NA if criteria are met.

All participants will have sparse PK sampling on Day 1 and at Weeks 4, 12, and 24 (and at early withdrawal). All participants who consent to participate in the intensive PK substudy (optional) will undergo intensive PK sampling at Week 4.

All participants will be monitored closely during the follow-up phase and, if applicable, should restart NA treatment in accordance with the NA re-treatment criteria mentioned below.

Prior to Protocol Amendment 5, randomization within each panel was stratified by Fibroscan score (<7 kPa vs  $\geq$ 7 kPa). Randomization and stratification are not applicable anymore per Protocol Amendment 5.

A participant will be considered to have completed the study if he or she has completed the assessments at Follow-up Week 48. The follow-up phase will be extended by 24 weeks (ie, up to Follow-up Week 72) for participants who are receiving optional treatment with PegIFN- $\alpha$ 2a and who meet NA treatment completion criteria at the end of treatment with NA + PegIFN- $\alpha$ 2a.

An Independent Flare Expert Panel (IFLEP) will be appointed for this study.

